1.3 Benefit / Risk Aspects

Benefits

Subjects enrolled in the present trial will be closely monitored and they will have the same or more frequent visits to the hospital compared to routine treatment, depending on local practice. During these visits the subjects will be given instructions regarding lifestyle changes (including limiting fluid intake). For some subjects the implementation of lifestyle changes might be enough to reduce bothersome nocturia, defined as 2 or more nocturnal voids.

Risks

Treatment of nocturia due to NP with desmopressin implies a prolonged antidiuretic effect that may be associated with an increased risk of developing hyponatraemia, especially in elderly patients. FE 201836 is designed to preserve potency at the V₂-receptor at the same level as desmopressin, with a shorter half-life, increased selectivity, faster clearance and greater extra-renal clearance compared to desmopressin. Based on the low degree of unchanged renal excretion of FE 201836, renal impairment is not expected to have any clinically relevant impact on the duration of the antidiuretic effect.

An improved safety profile is expected to result from this combination of characteristics. The short half-life of FE 201836 (approximately 2 hours) and low degree of unchanged renal excretion (approximately 5%) are designed to limit the antidiuretic effect to the night-time sleep period, when subjects do not drink or their fluid intake is limited to a minimum (to satisfy thirst only). Therefore, the risk for dilutional hyponatraemia that may occur after the subject starts drinking in the morning is expected to be low.

Subjects in the phase 1 clinical trial 000195 were dosed with up to 4800 µg (i.e., 9.6 times higher than the suggested maximum dose in the present phase 2 trial) orally without any subject being hyponatraemic. Pharmacokinetic/pharmacodynamic (PK/PD) modelling suggests that the duration of antidiuretic effect at 500 µg will be approximately 6 hours, limiting the potential for daytime antidiuresis.

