4.1 Study Overview

Subjects will be interviewed by telephone within 2-weeks of exiting the trial; those who withdraw early will not be interviewed. Clinical Outcomes Solutions will monitor all subject recruitment via weekly update reports from Quintiles to allow for arrangement with sites to conduct the exit interviews with subjects as they are finishing the trial.

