5.3 Quantitative Data

Data produced from the exit interviews will include improvement in nocturnal voids as well as levels of improvement and severity on items and domains on the NI Diary. Quantitative responses on the prospective and retrospective perceptions of improvement will be included in this evaluation, with the intent to code these responses for triangulation to the clinical trial results. As such, the following variables will be generated from the exit interviews:

- Subject exit interview data at Week 12, including the following:
 - Satisfaction will be evaluated using two methods to understand the distribution of the concept of satisfaction in this population and the relationship with nocturnal void frequency improvement.
 - Comparison of subjects stratified by the absolute response to the “Patient’s Global Impression of Improvement” (PGI-I) item.
 - Comparison of subjects who indicated that they are “very satisfied” or “somewhat satisfied” with improvement with those who indicate that they are “somewhat dissatisfied” or “very dissatisfied.”
 - PGI-I comparison between subjects who indicated that they feel “a great deal better,” “much better,” or “a little better” to those who indicated that they feel “a little worse,” “much worse,” or “a great deal worse.”
 - Patient’s Global Impression of Severity (PGI-S comparison between subjects who indicated that they are experiencing “none,” “mild,” “moderate,” and “severe” symptoms).

For perceived improvement in nocturnal voids, subjects will be categorized by change from “no” to “yes” from Baseline to Week 12. For subject interviews, which will be conducted between Weeks 12 and 14, subjects will be categorized by reported improvement as well as satisfaction with improvement in nocturnal void frequency.

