2.4 Important Notes to the Interviewer

Do not lead the subject, we want their open responses. Do probe where appropriate. Cover all the main parts of the interview guide, it is not critical that it flows in the order given, especially if something comes up earlier on in your discussions.

Any medical questions that a subject may raise just explain that you are not a medical professional and that she/he should speak to a physician.

Allow subjects enough time to answer the questions, especially as this is a telephone interview and you cannot observe any non-verbal cues.

3 Discussion Topics

NB: Please remember to allow subjects to respond spontaneously to the following questions, however, do encourage the subject to talk more about the issues that they raise. Probes have been included to help with this but only use when a Subject has not spontaneously mentioned the relevant issue(s).

Some key probes that you can use:

- Tell me more about that?
- How does it make you feel?
- Can you talk more about?
- Is it always like this?

Part 1: Experience of living with nocturia and its impact (15 minutes)

Introduction by interviewer: *So in this first part of the interview I'd like to start by asking you about your nocturia and how it impacts your day-to-day life. In particular, I'd like to ask you about how your nocturia affects you now, now that you have completed the clinical trial you have just been part of, and then I'd like you to think back to the time before the clinical trial and tell me how your nocturia affected you then. After that, I'm going to ask you to tell me about any change you may have experienced over the clinical trial.*

Firstly, how long is it since you finished the trial?

1. **Okay thinking about now that you have completed the clinical trial you have just been part of, can you tell me about how your nocturia is, now?**

[Try to focus the subject on discussing the symptoms of nocturia, rather than its impact].

- a. What is it like?
- b. What physical things do you experience?
- c. Thinking about a typical night now (*having completed the trial*), how many times do you typically get up in the night to urinate?

2. **Can you tell me about how your nocturia impacts your life now?**

[Encourage the subject to spontaneously mention the different ways nocturia impacts them. If any of the areas below are not mentioned, then probe specifically on these].

- a. Too little sleep?
- b. Problems with falling back to sleep?
- c. Tiredness?

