INSTRUCTION TO INTERVIEWER: MAKE A NOTE OF HOW MANY POINTS THE SUBJECT WOULD LIKE TO SEE CHANGE ON EACH 'MUST IMPROVE' IMPACT (PROBES D AND E ABOVE). ADD TOGETHER ALL OF THE RESPONSES TO PROBES D OR E AND USE IN Q11.

- 11.** You want to see improvement on [number of impacts mentioned in Q8c] things, and you stated a [THE RANGE OF POINT CHANGES] would be meaningful on each. So, would a [TOTAL OF RESPONSE TO PROBES D AND E ABOVE] change be meaningful?

Part 3: Discussion about nocturnal frequency and meaningful change (10 minutes)

Introduction by interviewer: *Okay, so now I'm going to ask you to discuss how often you get up at night to urinate and what sort of change in frequency would be important for you.*

As you may recall, you completed a diary for 3 days before each clinical trial site visit to report how many times you got up at night to urinate. The average number of times you went to the bathroom at night over these 3 days was then worked out (eg, if you had three events the first night, two the 2nd night and one the 3rd night, your average times of going to the bathroom at night to urinate would be two times).

12. As we just discussed, before the clinical trial you got up at night to urinate X times per night on average (see response to Q3c) and at the end of the clinical trial it was X times per night on average (see response to 1c). This means you had a X unit reduction/increase/same.

Instruction to interviewer: Check that score change is the same as what was discussed during Q5. If there is a reduction go to Q12a–d. If there is not a reduction go to Part 4.

- a. What does it mean for you to go to the bathroom at night, on average, X times less now than before the trial?
- b. Is this an important change for you?
- c. How do you feel because you go to the bathroom at night X times less now?
- d. What are you able to do because of this change in how often you go the bathroom at night?

Instruction to interviewer: if the change is more than one event, ask about the meaningfulness in one unit reduction and repeat questions a and b above; for example, if the subject had a score change of three, ask them:

- *Would two less events be meaningful? Why, why not?*
- *How would you feel or what could you do if you had two less events per night?*
- *How about one less event, would that still be meaningful? Why, why not?*
- *How would you feel or what could you do if you had one less event per night?*

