Part 4: Rating of change on the patient global assessment of change and patient global impression of severity (5 minutes).

Introduction by interviewer: *So in this final section, I'd like to get your responses to a few other questions that ask you about your overall impression of how your nocturia has been and how it may have changed. I will read the questions and response options to you and ask that you select the response that best reflects your experience.*

13. Overall, how satisfied are you with how the study medication relieved your nocturia?

- a. Choose from: "Very satisfied," "Satisfied," "Somewhat satisfied," "Neither satisfied nor dissatisfied," "Dissatisfied," "Somewhat dissatisfied," or "Very dissatisfied"
- b. Why did you select that response?
- c. What were you thinking about to make you select X?

14. Thinking back over the course of the clinical trial, would you say your overall health status was?

- a. Choose from: "Very much improved," "Much improved," "Minimally improved," "No change," "Minimally worse," "Much worse," or "Very much worse"
- b. Why did you select that response?
- c. What were you thinking about to make you select X?

15. Check the one number that best describes how your night time urination is now (based on the past 24 hours) (PGI-S)

- a. None
- b. Mild
- c. Moderate
- d. Severe

16. Check the one number that best describes how your night time urination is now, compared with how it was before you began taking medication in this study. (PGI-I Revised)

- a. Very much better
- b. Much better
- c. A little better
- d. No change
- e. A little worse
- f. Much worse
- g. Very much worse

That is the end of the interview today. Do you have any final questions? Thank you so much for taking part today and spending time with me in answering these questions.

Appendix 2

Statistical Design and Operating Characteristics

Trial Code: 000233

**Randomized Dose-Response Trial Investigating 6 Different Oral Doses of
FE 201836 for the Treatment of Nocturia due to Nocturnal Polyuria in Adults**

*Prepared for Ferring
By Berry Consultants, LLC
December 16, 2016*

1 Introduction

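### Exit-interview Q12 treats a count of voids 'now', after study drug has stopped, as the end-of-trial value and uses it to decide who is asked about meaningful change

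*Protocol*

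**What the plan says.** **Timing.** Study drug is dispensed at Visits 2, 4, 5, 6 and 7 (Protocol Table 6-1; SAP 9.1.1.1). Visit 8 only collects it (Protocol 6.7). The interview follows: "Subjects will be interviewed by telephone within 2-weeks of exiting the trial" (Appendix 1, section 4.1; Protocol 10.3.1.2 counts 14 days from Visit 8).

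**Void count.** Q1 opens with "Okay thinking about now that you have completed the clinical trial you have just been part of", and Q1c asks for the usual number of night-time voids in that present state. Q12 reuses the answer: "and at the end of the clinical trial it was X times per night on average (see response to 1c". The other value in the comparison is Q3c, a recalled count from before the trial.

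**Routing.** "If there is not a reduction go to Part 4". This skips Q12a-d. The interviewer is told to check the change against Q5, but not what to do if the two disagree.

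**Global ratings.** Q15 (PGI-S) asks about "how your night time urination is now (based on the past 24 hours". Q16 (PGI-I) compares the present with the time before study medication. Appendix 1, section 5.3 heads these data "Subject exit interview data at Week 12, including the following", although the same section places the interviews between Weeks 12 and 14.

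**Pharmacology (Protocol 1.3).** "The short half-life of FE 201836 (approximately 2 hours", and "duration of antidiuretic effect at 500 µg will be approximately 6 hours".

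**The concern.** The guide's own Part 1 introduction separates three frames: the present, the time before the trial, and change over the trial. Q12 needs the third but is filled from the first. For a short-acting drug taken nightly, the present after completion is an untreated state unless the interview comes very soon. A subject who improved because of the drug may have lost that improvement by then.

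Exit-interview objective 3 (what void reduction matters to patients, added at FDA request) and objective 4 (mapping interviews to trial data) are at stake. The error also has a direction. Change due to drug is what stopping removes, whereas change due to lifestyle or placebo response may remain. The subjects most likely to be routed past Q12a-d, or to discuss too small a change, are therefore drug responders.

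**Working it through.** **1. The plan's own figure.** Appendix 1, section 4.2 gives 16 per arm (96 in total) for 8.28 NI Diary points and 11 per arm (66 in total) for 10.30 points. With SD 10, correlation 0.40 and two-sided alpha 0.05, the SD of the difference is 10 × √(2 × (1 − 0.40)) = 10.95. The noncentral-t power is 0.8066 for n = 16 and 0.8021 for n = 11, against stated values of 0.807 and 0.802. Multiplying by 6 gives 96 and 66. These figures reproduce. They rest on the NI Diary Total Score, not on voids, so this point does not change them.

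**2. Reference period of each item.**

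| Item | Period asked about | Use |
|---|---|---|
| Q1c | present, trial completed | end value in Q12 |
| Q3c | before the trial, recalled | start value in Q12 |
| Q5, Q6 | change over the trial or since starting treatment | Q5 is the cross-check for Q12 |
| Q8-Q11 | NI Diary items and size of change | asked of everyone, independent of Q1c |
| Q12a, Q12c | fewer voids at present than before | only after a computed reduction |
| Q13, Q14 | study medication; course of the trial | Part 4 |
| Q15, Q16 | present | treated as Week 12 data |
| Visit 8 e-Diary | voids over 3 days before the visit; PGI-S and PGI-I the day before | on treatment |

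The Part 3 introduction describes the 3-day diary average, yet Q12 fills both values from recall. The interviewer asks how long ago the subject finished the trial, but no rule uses the answer.

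**3. How far off drug.** Remaining fraction = 0.5^(hours/2).
- 24 h: 12 half-lives, 0.5^12 = 0.024%.
- 7 days (168 h): 84 half-lives.
- 14 days (336 h): 168 half-lives.

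Half-lives alone do not settle the matter, because with nightly dosing the drug is almost cleared each day even on treatment. Undosed nights matter more. Assume the last bedtime dose is the night before Visit 8. The number of undosed nights then equals the days since Visit 8: 0 on the day of the visit, 1 a day later, 7 after a week, 14 at the limit. Q15's 24-hour window covers a dosed night only at the very start of that range. Q1c shifts more gradually, as undosed nights accumulate. The 14-day limit is twice the 1-week washout after which at least 2 voids are again required at Visit 4.

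**4. Effect on Q12.** Let C be the reduction on treatment and r the part lost by the interview. If recall is otherwise exact, Q12 computes C − r.
- If r ≥ C, the subject goes to Part 4.
- If 0 < r < C, the subject discusses a change too small by r.
- Illustration of the first case, with invented values: 3.0 before, 1.0 on drug, 3.0 at interview. The diary change is 2.0 and the Q12 change is 0.
- On a scale closer to the plan: the largest maximum effect versus placebo in its simulation scenarios is 0.6 voids. If r = 0.6, a subject is skipped when C ≤ 0.6 and otherwise understated by 0.6.

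**5. Numbers left.** The documents give no misrouting rate. If 25%, 50% or 75% of the initial 66 were routed to Part 4 (assumed), 66 × 0.75 = 49.5, 66 × 0.50 = 33 or 66 × 0.25 = 16.5 would answer Q12a-d.

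**The case against.** The other side has a good case on reach.

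- Appendix 1, section 4.4 wants interviews as soon as possible after exit, so 14 days is an outer limit. About 24 hours after the last dose, the most recent night is still a dosed one. This stands: the effect depends on a delay the documents do not give.
- Every subject is asked Q5, which covers how much better the nocturia became and what that meant. Q6, Q13 and Q14 are also framed on the trial or the study medication. This stands. A reader might infer that a misrouted responder yields no data on improvement, but only Q12a-d is lost.
- Section 4.2 makes the NI Diary threshold the primary goal, and Q8-Q11 serve it without Q1c. This stands.
- A reader might infer that off-drug ratings displace the anchor-based thresholds. The documents do not say so. Visit 8 e-Diary PGI-S and PGI-I are on treatment, and the anchor analyses belong to a separate Psychometric Analysis Plan that is not among the documents.
- Any reduction, including one without drug, can inform what size matters, and Q12 has step-down probes. This stands in part: subjects with no computed reduction never reach those probes.
- The half-life is stated for FE 201836 only. None is given for desmopressin, and placebo subjects have no drug effect to lose.

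The Q5 check does not answer the point, because the guide never says which answer decides the routing.

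**Conclusion.** The point holds as a flaw of reference period and routing. Followed as written, Q12 can label an off-drug count as the end-of-trial result, understate a drug responder's change, or bypass the only structured questions on the size of a meaningful void reduction. Q15 and Q16 have the same mismatch with the Week 12 label.

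It weakens exit-interview objectives 3 and 4. The stronger conclusion, that they cannot be met or that essentially all drug-specific change is missed, is not supported: several items still capture on-trial change, early interviews may reflect dosed nights, and the misrouted share is unknown.

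The conclusion assumes that some interviews fall more than a day or so after the last dose, and that voids drift back once drug stops, as the plan's own washout presumes. The primary endpoint, dose-response analysis and safety analyses are untouched.

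**What to change.** 1. Anchor Q1c (or an added item), Q12 including the present-tense wording of Q12a and Q12c, Q15 and Q16 to the last nights on study medication.
2. Fill Q12 from e-Diary means. Use Visit 8 for the end value. Give the start value a label that matches its visit: Visit 4 worded as *just before you started the randomised treatment*, or Visit 2 worded as *before any study medication*. Calling the Visit 4 mean a pre-trial value would create a new mismatch, since it follows lifestyle changes, run-in and washout.
3. State that the diary change decides the routing when it differs from recall.
4. If ratings of the present state are kept, label them off-treatment, and use the Visit 8 e-Diary PGI-S and PGI-I for mapping to Week 12 data.

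The cost is revised wording and two values passed to the interviewer. The site Case Report Form is a natural route, but its content is not shown (Appendix C), so confirm that it can carry them. The downside is up to 14 days' recall of the last treated nights, which the diary values help to anchor. No new visits or subjects are needed.

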1.1 Background

This document describes the statistical design of Ferring's randomized dose-response trial investigating 6 different oral doses of FE 201836 for the treatment of nocturia due to nocturnal polyuria in adults. The trial will also include a placebo control arm, and an active comparator arm of desmopressin that will serve as a benchmarking arm. This is a top-down design, meaning that subjects will initially be assigned to the placebo control and the highest dose of FE 201836. After this initial randomization, there will be an interim analysis. If, at that first interim analysis, there is a sufficient probability that the high dose of FE 201836 is effective, the 5 lower doses of FE 201836 will be opened with the objective of characterizing the dose-response curve.

This document describes the features of the simulated design, including the statistical models, decision rules, and simulation scenarios as input into the FACTS (Fixed and Adaptive Clinical Trial Simulator) software. Operating characteristics for the design are also summarized.

1.2 Primary Endpoint

The primary endpoint is the mean change from baseline in the number of nocturnal voids. This is defined as the average change from baseline across measurements taken at 1, 4, 8, and 12 weeks. The average change, inclusive of all measurements, is the final endpoint measurement and therefore the final primary endpoint value will be known at 12 weeks. A lower response indicates fewer voids as compared to baseline and is therefore a subject improvement.

1.3 Treatment Arms

The trial will enroll a maximum of 300 subjects. Subjects will be randomized to potentially one of 8 treatment arms including a control arm, 6 doses FE 201836 and an active comparator. We label these treatment arms as: d = 0 (control), 1, 2, 3, 4, 5, 6 (FE 201836), AC (active comparator). The expected dose levels of FE 201836 are 50, 100, 150, 250, 350, and 500 µg.

Trial Code: 000233

2 Statistical Modeling

This section describes the statistical modeling of the primary endpoint. All modeling is Bayesian in nature.

2.1 Final Endpoint Model

Let Y_i be the final primary endpoint value for the i th subject at 12 weeks. We model these outcomes for $d = 0, \dots, 6$ as

$$Y_i \sim N(\mu_d, \sigma^2)$$

where μ_d is the mean response for arm d . The active comparator arm is considered separately. We model the dose-response relationship for $d = 0, \dots, 6$ using a sigmoidal (E_{\max}) model as follows:

$$\mu_d = \alpha_1 + \frac{(\alpha_2 - \alpha_1)v_d^{\alpha_4}}{v_d^{\alpha_4} + \alpha_3^{\alpha_4}}$$

where v_d is the effective dose strength ($v_0 = 0, v_1 = 0.5, v_2 = 1, v_3 = 1.5, v_4 = 2.5, v_5 = 3.5, v_6 = 5$). The four parameters are interpreted as:

- α_1 is a constant offset, i.e. the response when the effective dose strength is 0.
- α_2 is the maximum response that the model asymptotically approaches as the effective dose strength tends to infinity.
- α_3 is the effective dose strength for the ED50. The ED50 is defined as the dose for which the response is half of the maximum response.
- α_4 is the slope parameter.

These parameters are modeled with prior distributions:

$$\alpha_1 \sim N(-1, 3^2)$$

$$\alpha_2 \sim N(-0.5, 2^2)$$

$$\alpha_3 \sim N^+(2, 2^2)$$

$$\alpha_4 \sim N^+(5, 3.5^2)$$

The error variance is modeled as:

Trial Code: 000233

$$\sigma^2 \sim IG(0.5, 0.605)$$

The notation $N^*(\mu, \sigma^2)$ refers to a positively truncated normal distribution. The $IG(a, b)$ is the inverse gamma distribution defined by:

$$f(x|a, b) = \frac{b^a e^{-b/x}}{x^{a+1} \Gamma(a)}$$

2.1 Adjustments in Primary Analysis

The primary analysis applied to actual trial data will be adjusted for the number of baseline voids x_0 . This implies that the actual fitted dose-response model for subject i will be

$$\mu_{d,i} = \beta x_{0,i} + \alpha_1 + \frac{(\alpha_2 - \alpha_1) v_d^{\alpha_3}}{v_d^{\alpha_3} + \alpha_3^{\alpha_3}}$$

The prior distribution for β is modelled as

$$\beta \sim N(0, 10^2)$$

For the purposes of evaluation of trial design and operating characteristics, the model without the adjustment for number of baseline voids will be fitted to simulated trial data.

